9.3.5 Withdrawal of Subjects from the Study

Subjects may voluntarily withdraw consent to participate in the study for any reason at any time.

Withdrawal of consent occurs when a subject does not want to participate in the study anymore and does not want to attend any further visits or assessments, have further study-related contact, or allow analysis of already obtained biologic material.

If a subject withdraws consent, the investigator must make every effort to determine the primary reason for this decision and record this information. Investigational treatments must be discontinued and no further assessments conducted. All study participation for that subject will cease and data to be collected at subsequent visits will be considered missing.

All biological material that has not been analysed at the time of withdrawal may be used, unless consent for its use is withdrawn in writing. Further attempts to contact the subject are not allowed unless safety findings require communication or follow-up.

Under the following circumstances the subject MUST be withdrawn from the study:

1. Withdrawal of informed consent
2. Any safety reasons, clinical AE, laboratory abnormality, or intercurrent illness which, in the opinion of the investigator or sponsor indicates that continued participation in the study is not in the best interest of the subject
3. Exogenous testosterone use or additional monitoring of testosterone levels that inadvertently unblinds the subject's study arm allocation
4. Severe non-compliance to the protocol, as judged by the investigator and/or sponsor
5. Treatment code or unblinding prematurely broken by the investigator
6. Termination of the study by the sponsor
7. Loss of ability to freely provide consent through imprisonment or involuntarily incarceration for treatment of either a psychiatric or physical (e.g., infectious disease) illness.

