9.3.4 Study Drug Interruption and Discontinuation

Subjects may voluntarily discontinue investigational treatment for any reason at any time.

At the time of study drug discontinuation, the subject should have (as soon as possible) an EOT visit with the assessments that are normally done at the Week 48 visit (EOT, Visit 7). This should take place within 7 days after discontinuation of study drug. The reason for the discontinuation must be documented in the subject's medical records and entered on the appropriate electronic case report form (eCRF) page. All subjects who discontinue the study drug should enter the FU phase and attend the final follow up visit 12 weeks after EOT (FU, Visit 8).

Subjects will in addition be asked to provide a plasma and semen sample for PK at EOT (Visit 7), unless they are not able to provide this sample. This applies also to a subject discontinued because of elevated testosterone as determined by an unblinded physician. The investigator and study staff must discuss with the subject, the subject's continued participation in the study and request subjects to continue attending FU visits according to the study visit schedule.

If the subject cannot, or is unwilling to attend the FU visits, the site staff should request maintenance of regular phone contact with the subject, or with a person pre-designated by the subject. This phone contact should preferably be performed according to the study visit schedule. Data concerning the subject's health status, including information regarding new/concomitant treatments, AEs, AESIs (i.e., rash), and vital status will continue to be collected.

The investigator must also contact the IRT to register the subject's discontinuation from investigational treatment.

If the subject temporarily discontinues study drug because of AE or SAE or other relevant issue, the investigator should attempt to restart it as soon as possible after circumstances allow and in agreement with the Medical Monitor.

Investigational treatment MAY be permanently discontinued under the following circumstances:

1. Significant worsening of lower extremity oedema
2. Significant worsening of obstructive urinary symptoms

Investigational treatment MUST be permanently discontinued under the following circumstances:

3. If subject develops fragility fracture.

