12.1.6 Partner Pregnancies

Pregnancy outcomes must be collected for the female partners of the subjects who took study treatment in this study. Pregnancy itself is not regarded as an AE unless there is suspicion that the study drug may have interfered with the effectiveness of a contraceptive medication. If a pregnancy is reported for a subject's partner, study drug will be immediately discontinued. The outcome of all pregnancies (spontaneous miscarriage, elective termination, normal birth or congenital abnormality) must be followed up and documented. Follow up should be performed up to delivery and examination of the new-born, after which a follow-up report should be sent with any new information regarding the pregnancy and the outcome of the birth. After study drug discontinuation, the subject should continue with all study schedule assessments, except study drug administration. The male study subject has to continue to wear a condom for at least 3 months after the last medication intake. Unprotected intercourse with his pregnant partner presents a risk of toxicity to the unborn child.

All congenital abnormalities/birth defects should be classified as SAEs. Spontaneous miscarriages should also be reported and handled as SAEs. Elective abortions without complications should not be handled as SAEs, but should be reported as AEs.

Pregnancies must be reported to ICON Pharmacovigilance and Safety Services using the reporting details and timelines provided in [Section 12.1.8](#) within 24 hours of awareness.

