12.4 DEXA Scan

Bone density will be evaluated with standard procedure described in study imaging manual. All evaluations during the study for particular subject should, where possible, be performed on the same machine with particular attention to ensuring consistency in positioning patients.

To assess the spine, the subject will be in supine position with legs supported on a padded box to flatten the pelvis and lower (lumbar) spine. To assess the hip, the foot is placed in a brace that rotates the hip inward. The detector will be slowly passed over the area separately for spine and hip, generating images. The duration of examination will be up to 30 minutes. DEXA T Score will be calculated based on actual measured bone density value. Both values will be evaluated for safety.

EOT DEXA scan: If the subject is discontinued from the treatment early, DEXA will be performed only if they reached minimum Week 36 (Visit 4) active treatment period. In order to accommodate scheduling, EOT DEXA can be performed within 5 days before the EOT visit

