13.5.2 Analysis of Primary Endpoint

The percentage change from Baseline in lumbar bone mineral density measured in g/cm² by DEXA will be summarised by dose group and visit. A single sample 1-sided t-test conducted at the 2.5% significance level will be used to analyse percentage change from Baseline (MBGS205) at Week 48 (MBGS206) in each treatment arm to test the null hypothesis that the percentage decrease from Baseline is $\leq 3\%$. Only subjects that have a post-Baseline DEXA assessment in MBGS206 will be included in this analysis.

The primary analysis will be performed using the safety population.

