### 8.2 Subject disposition

All subjects who entered the extension study will be included in a summary of subject accountability. The number of subjects entering the extension study, the frequency and percentage of subjects randomised, in the Safety population, in the ITT population and in the PK population will be summarised by treatment regimen and overall.

Subject disposition information will be summarised by treatment regimen and overall. The number of subjects completing and withdrawing from the treatment period (up to and including Visit 7) and the number of subjects completing and withdrawing from the study will be tabulated. Reasons for treatment discontinuation and discontinuation from the study will also be presented.

The follow-up time will be summarised descriptively.

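### Protocol 9.3.5 items 3–5 require withdrawal from the study, not only from drug, for men who may still consent, and do not say whether the EOT and follow-up visits in 9.3.4 apply to them

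*Protocol*

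**What the plan says.** Two adjacent protocol sections deal with men who stop early.

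- **Section 9.3.4 (drug discontinuation).** The man has an EOT visit within 7 days of stopping drug, with the Week 48 assessments. Then: "All subjects who discontinue the study drug should enter the FU phase and attend the final follow up visit 12 weeks after EOT". If he will not attend, the site asks to keep in touch by telephone.
- **Section 9.3.5 (study withdrawal).** It first defines withdrawal of consent and its consequences, and then begins a list: "Under the following circumstances the subject MUST be withdrawn from the study". Item 1 is withdrawn consent, item 2 a safety judgement that continued participation is not in the man's interest, item 6 sponsor termination and item 7 loss of the ability to consent. Items 3–5 are exogenous testosterone or unblinding testosterone monitoring, severe non-compliance, and a treatment code prematurely broken by the investigator. No visit is attached to items 3–5, and 9.3.4 is not mentioned.

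The plan treats the two outcomes as distinct. SAP 8.2 states: "Reasons for treatment discontinuation and discontinuation from the study will also be presented".

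For a man who stops early, protocol 12.4 limits the scan: "DEXA will be performed only if they reached minimum Week 36 (Visit 4) active treatment period". Protocol 13.5.2 ties the primary analysis to that scan: "Only subjects that have a post-Baseline DEXA assessment in MBGS206 will be included in this analysis". SAP 8.6.2 repeats the condition.

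**The concern.** A man who took testosterone, was severely non-compliant or had his code broken has not necessarily refused further visits. If a site treats 9.3.5 as ending his participation, two things can be lost.

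- **The EOT DEXA, if he reached Week 36.** Within MBGS206 the only scan after baseline is the one at EOT (protocol Table 9–1). Without it he is outside the primary bone density analysis. He is also outside the SAP's ITT population, which requires a post-baseline MBGS206 lumbar value (SAP 6.1).
- **The follow-up visit 12 weeks after EOT (nominally Week 60), at whatever point he stopped.** It carries haematology, chemistry, PSA, blood pressure and total testosterone. Adverse event recording to 90 days after the last dose (protocol 12.1.2, 12.1.8) continues but does not replace those measurements.

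The same conduct can fall under either section. Missing four or more consecutive doses is a drug stop in 9.3.4 (item 7), yet may also be called severe non-compliance under 9.3.5. An investigator may unblind at once in an emergency (10.2.4, 10.3), and the protocol does not say whether that counts as a premature code break.

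**Working it through.** **1. The two rules compared, for a consenting man under items 3–5**

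| Question | 9.3.4 | 9.3.5, items 3–5 |
|---|---|---|
| Does he stop drug? | Yes | Yes, by implication |
| EOT visit? | Within 7 days | Not stated |
| Follow-up visit? | 12 weeks after EOT | Not stated |
| Does he remain in the study? | Yes | No; withdrawal is mandatory |
| Cross-reference to the other section? | None | None |

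He meets the wording of both sections, and no sentence says which governs. When the protocol wants a man followed off drug it can say so. After a partner pregnancy, 12.1.6 says: "After study drug discontinuation, the subject should continue with all study schedule assessments, except study drug administration". That event is itself a 9.3.4 stop (item 13), so it shows the protocol's usual practice and not a second conflict.

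**2. The plan's own figure**

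The synopsis enrols 30 men per previous active arm, assumes about 17% dropout and aims for about 25 completers. 30 × 0.83 = 24.9, and 25 / 0.83 = 30.1. The figure reproduces. Scans from early stoppers come on top of the planned 25.

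**3. Ceilings on scans at stake, per dose**

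- Early stops: 0.17 × 30 = 5.1 men.
- Assumption: stops are spread evenly over Weeks 24–48, Day 168 to Day 336, which is 168 days.
- Before Week 36 there is no EOT DEXA under either section.
- Stops after Week 36 (Day 252): 5.1 × 84/168 = 2.55.
- SAP Appendix F opens the Week 48 DEXA window at Day 308 and closes the Week 24 window at Day 196. A scan on Days 197–307 fits neither. If that window governs the primary analysis, the in-window stops number 5.1 × 28/168 = 0.85. Allowing 7 days to the EOT visit and 5 more to the scan, stops from Day 296 count: 5.1 × 40/168 = 1.21.

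These ceilings place every early stop under items 3–5.

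**4. Assumed shares of stops falling under items 3–5**

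The documents give no share, so 10%, 25% and 50% are shown as a range. The shift in a dose mean is k × 2 / (25 + k), where k is the number of scans. It assumes that these men's mean change differs by 2 percentage points, in either direction.

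| Share of stops | Scans in window | Shift (points) | Scans after Week 36 | Shift (points) | Week 60 visits |
|---|---|---|---|---|---|
| 10% | 0.09 | 0.007 | 0.26 | 0.020 | 0.5 |
| 25% | 0.21 | 0.017 | 0.64 | 0.050 | 1.3 |
| 50% | 0.43 | 0.033 | 1.28 | 0.097 | 2.6 |
| 100% (ceiling) | 0.85 | 0.066 | 2.55 | 0.185 | 5.1 |

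Example: 0.64 × 2 / 25.64 = 0.050.

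**5. Precision**

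The 95% t half-width is 0.413 SD with 25 men and 0.404 SD with 26. One extra scan therefore narrows it by about 2%.

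**6. What this leaves open**

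SAP 8.6.2 tests Week 48 values with LOCF and does not mention the Appendix F windows, while SAP 8.7.1 applies them to DEXA analyses. How a scan on Days 197–307 would enter the primary test is not settled, which is why both columns of scans are shown.

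**The case against.** The strongest reply is that 9.3.4 already covers these men. It speaks of all subjects who stop drug, every man under items 3–5 stops drug, and nothing in 9.3.5 exempts him. That reading is available, and it is why this point is a conflict of rules and no more. It does not remove the conflict, because 9.3.5 still says that he must leave the study.

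A reader might infer several stronger claims. The documents do not support them.

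- **That 9.3.5 forbids visits.** The sentence "Investigational treatments must be discontinued and no further assessments conducted" follows a clause about a subject withdrawing consent. The sentence "Further attempts to contact the subject are not allowed unless safety findings require communication or follow-up" stands just before the list, but it closes the same run on consent and has a safety exception. Neither is written for items 3–5.
- **That item 2 is part of the fault.** It applies where continued participation is judged against the man's interest, which is a reasonable ground for ending visits. The main safety stops are already drug-only stops in 9.3.4.
- **That 11.2.1 contradicts 9.3.5.** One says that a man may be withdrawn for extra unblinded testosterone monitoring, the other that he must be. The 9.3.5 item is limited to monitoring that reveals his arm, so the two can coexist.

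It is also fair to say that a scan after exogenous testosterone is confounded, that all analyses are declared exploratory (protocol 13.5.1), and that hepatic and renal stops have their own follow-up rules. These points lower the stakes and justify an analysis flag. They do not explain why a consenting man's visits should be left in doubt.

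**Conclusion.** The point holds at low severity. Items 3–5 are a stated mandatory rule, and followed literally it ends the participation of men who may still be willing to attend.

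The size cannot be computed, because the documents give no number of such withdrawals. Well under one scan per dose is the likely order. It rests on the planned 17% dropout, evenly spread stops, and items 3–5 making up a minority of stops beside withdrawn consent, loss to follow-up, 9.3.4 stops and item 2. Only at the 50% share, and counting every scan after Week 36, does the figure pass one. The shifts in the mean also rest on an assumed 2-point difference and are small against the 3% threshold. Their sign is unknown, so no direction of bias should be claimed. Planned power rests on the 25 completers and is not at risk. The follow-up visit is the more frequent loss, since it can be missed whenever a man stops.

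**What to change.** Amend protocol 9.3.5 as follows.

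- Make items 3–5 reasons for permanent drug discontinuation followed, where the man consents, by the 9.3.4 EOT visit (DEXA under the existing Week 36 rule) and the follow-up visit 12 weeks later.
- Keep item 2 as study withdrawal only where the visits themselves are judged not in his interest, and handle other safety stops under 9.3.4.
- State that the bans on further assessments and on contact apply to withdrawn consent.
- In the SAP, flag data collected after exogenous testosterone or unblinding.
- Editorial: 9.2.1 points to 9.3.5 for the fragility-fracture stop, which is in 9.3.4.

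The visits are already in the schedule. The cost is one or two extra visits for a few men, the analysis flag, and a protocol amendment with ethics approval across approximately 50 sites.

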9.3.6 Procedures for handling subjects incorrectly enrolled or randomised

Subjects who fail to meet the inclusion/exclusion criteria must not be enrolled or randomised. If a subject not meeting the study criteria is randomised in error, a discussion must occur between the Medical Monitor and the investigator regarding whether to continue or discontinue the subject from the study. If agreement is reached, the subject should complete the study unless there are safety concerns or if the subject withdraws the consent.

9.3.7 Discontinuation of Study Sites

Study site participation may be discontinued if Mereo BioPharma or designee, the investigator or Institutional Review Board (IRB)/Independent Ethics Committee (IEC) of the study site judges it necessary for medical, safety, regulatory, or other reasons consistent with applicable laws, regulations, and GCP.

9.3.8 Discontinuation of Study

The study may be discontinued if Mereo BioPharma or designee, including through DMC recommendation, judges it necessary for medical, safety, regulatory, or other reasons consistent with applicable laws, regulation, and GCP.

9.3.9 Lost to Follow-up

All reasonable efforts must be made to locate subjects to determine and report their ongoing status. There should be three documented attempts to contact the subject. This includes follow-up with persons authorised by the subject. Lost to follow-up is defined by the inability to reach the subject after a minimum of 3 documented phone calls, faxes or emails, as well as a lack of response by the subject to 1 registered mail letter. All attempts should be documented in the subject's medical records. If it is determined that the subject has died, the site will use permissible local methods to obtain the date and cause of death.

If the investigator's use of a third-party representative to assist in the FU visit of the study has been included in the subject's informed consent, then the investigator may use a sponsor-retained third-party representative to assist site staff with obtaining subject's contact information or other public vital status data necessary to complete the FU visit of the study. The site staff and representative will consult publicly available sources, such as public health registries and databases, in order to obtain updated contact information. If, after all attempts, the subject remains lost to follow-up, then the last known alive date as determined by the investigators should be reported and documented in the subject's medical records.

10 TREATMENT OF SUBJECTS

10.1 Identity of Study Treatment(s)

Details of the study treatments are presented in [Table 10–1](#).

Table 10–1 Study Treatments

Drug Name	BGS649	BGS649 matched placebo
Active ingredient	BGS649	Not applicable
Strength(s)	[REDACTED]	Not applicable
Dosage Form	[REDACTED]	[REDACTED]
Route of administration	Oral	Oral
Mode of administration	With water	With water
Dose	[REDACTED] Possible doses are: [REDACTED] OR [REDACTED] OR [REDACTED]	

10.1.1 Administration of Study Treatment(s)

Subjects receiving active doses of BGS649 in Study MBGS205 will continue with the same dose in Study MBGS206 and the blind will be maintained. Subjects receiving placebo in Study MBGS205 will be randomised to receive BGS649 [REDACTED]. If one or more dosing arms are dropped during the conduct of Study MBGS205 these will not be progressed in Study MBGS206 and subjects switching from placebo will be randomly allocated to available dose arms. All doses should be taken orally by the subject, with water, on a [REDACTED] at approximately the same time. Treatment may be self-administered except at the Baseline visit of Study MBGS206 (Week 24 of Study MBGS205), when it must be taken by the subject at the study site.

10.2 Study Treatment Packaging and Labelling

10.2.1 Packaging

Each study site will be supplied with investigational treatment [REDACTED] and matching placebo, indistinguishable in appearance and taste) in three pack types [REDACTED] with packaging of identical appearance, consistent with [Table 10–1](#).

A unique medication number is printed on the label of each pack which corresponds to one of the treatment regimens. Investigator staff will identify the investigational treatment to dispense to the subject by contacting the IRT and obtaining the medication number(s). Records of subjects assigned medication numbers will be recorded in source documentation.

10.2.2 Labelling

Labels will comply with the legal requirements of each country and be printed in the local language. They will supply no information about the subjects. Packs are labelled for both MBGS205 and MBGS206. However, the IRT will not allow allocation of placebo packs to subjects in MBGS206.

10.2.3 Storage

Based on available stability data, BGS649 [REDACTED] packaged in Aclar blisters, should be stored below 25°C. The storage conditions for the study drug will be described on the medication label. Until dispensed to the subjects, the study drug will be stored in a securely locked area, accessible to authorised personnel only.

10.2.4 Blinding and Randomisation of Study Treatment(s)

Subjects receiving active doses of BGS649 in Study MBGS205 will continue with the same dose in Study MBGS206; this transfer will be handled by the IRT and the blind will be maintained.

Subjects receiving placebo in Study MBGS205 will be re-randomised at the Baseline visit to receive one of the 3 treatment regimens [REDACTED] in a 1:1:1 ratio. If one or more dosing arms are dropped during the conduct of Study MBGS205 these will not be progressed in Study MBGS206 and subjects switching from placebo will only be randomly allocated to available dose arms.

The investigator or his/her delegate will contact the IRT after confirming that the subject fulfils all the inclusion/exclusion criteria. The IRT will assign a medication number to the subject, which will be used to link the subject to a treatment regimen and will specify a unique medication number on the label of investigational treatment to be dispensed to the subject. The randomisation number will not be communicated to the caller.

The randomisation numbers will be generated using the following procedure to ensure that treatment assignment is unbiased and concealed from subjects and investigator staff. A subject randomisation list will be produced by ICON Biostatistics using a validated system that automates the random assignment of subject numbers to randomisation numbers. These randomisation numbers are linked to the different treatment regimens, which in turn are linked to medication numbers. A separate medication list will be produced using a validated system that automates the random assignment of medication numbers to packs containing the investigational drug.

Subjects, investigational staff, persons performing the assessments and data analysts (other than those described below) will remain blind to the identity of the treatments [REDACTED] from the time of randomisation until after database lock. The Sponsor and CRO personnel may be unblinded at the time of unblinding the MBGS205 study, in order to make development decisions. At this time, enrolment of MBGS206 will be completed and the opportunity to introduce a bias, minimal. In order to maintain the blind described above, testosterone, LH, FSH and oestradiol measurements will

be blinded to site and sponsor staff and monitoring will be performed by an independent unblinded physician.

The blind will be maintained using the following methods:

1. Randomisation data will be kept strictly confidential until the time of unblinding, and will not be accessible to anyone involved in the study
2. The identity of the treatments will be concealed by the use of investigational treatment that is identical in packaging, labelling, schedule of administration and appearance.

Should a situation arise where unblinding is required, the investigator at that site may perform immediate unblinding without the need for communication with the sponsor (see [Section 10.3](#)).

